7.3 Physical Examination

Abnormal findings in physical examinations will be listed (see Section [16.7](#)).

7.4 Vital Signs

The available parameters are: pulse rate, diastolic and systolic blood pressure, weight, temperature. These will be summarized using descriptive statistics (for actual values and changes from baseline).

A detailed list of tables and listings can be found in Section [14.9](#) and Section [16.10](#), respectively.

7.5 ECG

Investigator's conclusion on the ECG profile will be summarized descriptively.

A detailed list of tables and listings can be found in Section [14.8](#) and Section [16.9](#), respectively.

8 ANALYSIS OF PHARMACOKINETICS, PHARMACODYNAMICS AND DISEASE-RELATED MARKERS

8.1 Analysis of pharmacokinetics

The analysis of caplacizumab in plasma samples will be performed at PRA International using a validated method. The results of the analysis will be transferred to SGS Secure Data Office in Excel format. Individual pharmacokinetic concentrations will be reported in ng/mL. Concentrations will be converted to μ g/mL.

Individual study drug concentrations will be listed. In addition, a listing of the actual sampling times relative to the study drug administration times will be presented. Drug concentrations will be summarized by scheduled sampling time using descriptive statistics and will be listed and summarized in tabular and graphical form.

All analyses will be run on the safety population.

Pharmacokinetic concentrations and descriptive statistics will be reported to 3 significant digits for values up to, but not including 1000. Values equal to and above 1000 will be reported as the value without decimal signs.

A detailed list of tables, listings and figures can be found in Section [14.3](#), Section [16.3](#) and Section [15.3](#), respectively.

8.2 Analysis of pharmacodynamics

Available parameters: RICO activity, vWF:Ag concentration and FVIII:C activity.

The sample analysis of the pharmacodynamics samples will be performed at ACM using validated methods. The results of the analysis will be transferred to SGS SD Office in Excel format. Concentrations will be reported in % with one decimal.

RICO activity, vWF:Ag concentration and FVIII:C activity will be summarized using descriptive statistics and will be listed and summarized in tabular and graphical form.

RICO activity will also be categorized and represented as a frequency tabulation (number of subjects and percentages) by timepoint using following categories: <20% / ≥20%.

All analyses will be run on the safety population. Pharmacodynamic concentrations or activity and their descriptive statistics will be reported to 3 significant digits.

A detailed list of tables, listings and figures can be found in Section 14.4, Section 16.4 and Section 15.3, respectively.

8.3 Analysis of pharmacokinetics/pharmacodynamics

The planned population PK/PD analysis will be described in a separate data analysis plan. The results of this analysis will be reported in an independent Modeling and Simulation report.

A figure will be made of the RICO activity in function of the PK concentration/vWF:Ag ratio (for matching samples). The PK/vWF:Ag ratio will be expressed in molarity. The conversion factor to molarity for PK is given by PK concentration (ng/mL)/14. The conversion factor to molarity for vWF:Ag is given by vWF:Ag concentration (%) x 0.4.

8.4 Analysis of disease-related markers

ADAMTS13 activity levels (<10% / ≥10%) will be summarized by treatment group (Caplacizumab, Placebo, OL Caplacizumab) and by time point using the safety population.

The number and proportion of subjects with ADAMTS13 activity < 10% at Week 5 will be summarized by treatment group (Caplacizumab, Placebo, OL Caplacizumab) for the following subgroups: rituximab use during daily PE period: yes / no, other immunosuppressive treatment (not including rituximab) during daily PE period: yes / no. The effect of duration of daily PE will be analyzed by means of a logistic regression model with ADAMTS13 activity < 10% at Week 5 as dependent variable and treatment group (Caplacizumab, Placebo) and duration of daily PE as independent variables.

A series of 11 horizontal black bars of varying lengths, decreasing in length from top to bottom. The first 10 bars are evenly spaced, and the last bar is positioned below the 10th bar.

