Results from the caplacizumab arm suggest that ADAMTS13 activity data could identify subjects who were at risk for early relapse. In 7 of 8 subjects with a relapse in the first month, it occurred within 4-10 days after stopping caplacizumab. All 7 subjects had ADAMTS13 activity values <10% at baseline, during and near the end of the treatment period, indicating unresolved underlying disease activity. In the 8th subject, the relapse event occurred at 30 days after stopping caplacizumab treatment. This subject had normalization of ADAMTS13 activity during and near the end of the treatment period. However at the time of the relapse, ADAMTS13 activity was again suppressed <10%, which suggests a *de novo* TTP event. Conversely, 22 caplacizumab-treated subjects did not have an exacerbation or relapse, with ADAMTS13 activity data available near the end of the treatment period for 16/22 patients. In 13 of 16 subjects without exacerbation or relapse, ADAMTS13 activity had returned to values \geq 10% near the end of the treatment. ADAMTS13 activity results from the placebo treated subjects supported the potential predictive value of the marker: for 14 of 16 placebo subjects without exacerbation or relapse (ADAMTS13 data available for 16/23 placebo subjects), ADAMTS13 activity values were \geq 10% near the end of the placebo treatment period. A total of 11 placebo subjects had an exacerbation during the treatment period, and ADAMTS13 activity data were available for 8 of them. Seven of 8 placebo subjects with an exacerbation had ADAMTS13 activity <10% around the time of the exacerbation, while the 8th subject had a borderline ADAMTS13 activity value of 11%. In summary, the data support ADAMTS13 activity as a potential marker to identify patients at risk for exacerbation or relapse, specifically patients with signs of ongoing active disease during the treatment period who are at risk of relapse early after stopping caplacizumab treatment.

No significant unanticipated safety concerns were raised for treatment with caplacizumab in this study. The results were as expected for the population of patients with acquired TTP. The overall duration of exposure to study drug was similar in the two treatment arms.

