- Exacerbation is defined as recurrent thrombocytopenia after initial recovery of platelet count (platelet count $\geq 150 \times 10^9/L$ with subsequent stop of daily PE within 5 days), requiring re-initiation of daily PE, occurring during the first 30-days post-daily PE period.
- Relapse is defined as recurrent thrombocytopenia after initial recovery of platelet count requiring re-initiation of daily PE, occurring after the 30-days post-daily PE period.

^{**} For logistical reasons, the Sponsor needs to be contacted if the daily PE period exceeds beyond 30 days.

Based on the mechanism of action and the available efficacy and safety results from study ALX-0681-2.1/10 (Phase II TITAN trial) it is considered desirable from both a treatment and exposure perspective (to maximize the number of subjects exposed to caplacizumab), to allow for crossover to open-label caplacizumab for subjects who experience an exacerbation of the TTP episode.

Exacerbation

In case of a first exacerbation of the presenting TTP episode, subjects will receive open label caplacizumab together with daily PE irrespective of what the initial treatment allocation was. The blind will not be broken for the initial treatment allocation. Caplacizumab treatment and visit schedule will be the same as during the initial treatment period. In case a subject has subsequent exacerbations, standard of care treatment of daily PE and appropriate immunosuppressive treatment should be initiated as per site practice. There will be no re-initiation of study drug administration for a second or further exacerbation.

Relapse during the treatment extension period

In case a subject has a first TTP recurrence while still receiving study drug in the treatment extension period, then daily PE should be started as part of standard of care treatment together with appropriate immunosuppressive treatment. Study drug treatment will crossover as open-label caplacizumab irrespective of what the initial treatment allocation was, without breaking the blind of the initial treatment assignment. In case a subject has subsequent relapse, standard of care treatment of daily PE and appropriate immunosuppressive treatment should be initiated as per site practice. There will be no re-initiation of study drug administration for a second or further relapse.

Relapse during the 4-week FU period

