4.2.2 Calculation of percentages

Missing values will not be included in the denominator count when computing percentages.

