4.3.6 Presentation of treatment groups

The following treatment group labels will be used in the tables, listings and figures, unless specified otherwise:

- Caplacizumab
- Placebo
- Open-label (OL) Caplacizumab

Treatment groups Caplacizumab and Placebo refer to the initial treatment group prior to a potential switch to open-label caplacizumab, and only data up to the switch are used in the analyses of these treatment groups. The OL Caplacizumab treatment group will only be used for analyses after the switch to open-label caplacizumab.

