4.4 Analysis Periods and Visit Windows

4.4.1 Analysis periods

The following analysis phases are defined for this study: Screening, Treatment, Follow-up. Within these analysis phases, the following analysis periods and subperiods will be considered:

Table 1: Analysis periods

Period	Subperiod	Start period	End period
(Screening)		Date of signing the ICF, with 00:00 added as timepart	First DB treatment administration datetime – 1 min
Double-Blind (DB) Treatment	Daily PE	First administration datetime of DB treatment	Start of DB post-daily PE subperiod – 1 min
	Post-daily PE	Date of switch to post-daily PE + 1 day with 00:00 added as timepart	Min(Week 5 visit date if no treatment extension or last visit date of treatment extension period with 23:59 added as timepart, early termination visit date with 23:59 added as timepart, first administration datetime of OL treatment – 1 min)
	Daily PE	First administration datetime of OL treatment	Start of OL post-daily PE subperiod – 1 min

CONFIDENTIAL

Open-label (OL) Treatment	Post-daily PE	Date of switch to post-daily PE + 1 day with 00:00 added as timepart	Min(Week 5 visit date if no treatment extension or last visit date of treatment extension period, early termination visit date) with 23:59 added as timepart
(Follow-up)		End of treatment period + 1 min	Trial termination date, with 23:59 added as timepart

Note that the last analysis period in case of early termination will always be ended by the trial termination date.

The 'overall treatment period' corresponds with the treatment analysis phase and covers both the DB treatment analysis period and the OL treatment analysis period. Note that only subjects who experience a relapse or exacerbation will have an OL treatment analysis period. For these subjects, the overall treatment period starts at start of DB treatment period and ends at end of OL treatment period. For subjects with no switch to open-label caplacizumab, the overall treatment period starts at start of DB treatment period and ends at end of DB treatment period.

The 'overall study period' covers both the treatment analysis phase and the follow-up analysis phase.

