14.5 Disease related markers

Table 14.2.4.1: Disease related markers: Descriptive statistics of ADAMTS13 activity

Descriptive statistics of ADAMTS13 activity levels by treatment group and by time point.

Population: safety population.

Table 14.2.4.2: Disease related markers: Logistic regression: proportion of subjects with ADAMTS13 activity < 10% at Week 5.

Frequency tabulation of number and percentage of subjects with ADAMTS13 activity <10% including Logistic regression results on model with ADAMTS13 <10% at Week 5 as dependent variable and treatment group and duration of daily PE (including interaction) as independent variables. The analysis will be repeated for following subgroups:

-Overall

-Rituximab immunosuppressive use during daily PE yes/no

-Non-Rituximab immunosuppressive use during daily PE yes/no

Population: safety population.

Table 14.2.4.3: Disease related markers: Cox proportional hazards model: Time to sustained ADAMTS13 activity ≥ 10%.

Cox proportional hazards regression model with Time to sustained ADAMTS13 activity ≥10% as dependent variable. Time to sustained ADAMTS13 activity ≥ 10% is defined as 2 consecutive weekly visits during treatment or follow-up with reported ADAMTS13 activity ≥ 10% (first visit will be used to calculate time to event).

Following covariates will be tested:

-Rituximab immunosuppressive use during daily PE yes/no

-Non-Rituximab immunosuppressive use during daily PE yes/no

-Duration of daily PE

-Tapering of daily PE yes/no

Population: safety population.

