Study Visit	Week 1 Day 1 (1 day after last daily PE) (± 1 day)	Week 2 Day 8 (8 days after last daily PE) (± 1 day)	Week 3 Day 15 (15 days after last daily PE) (± 1 day)	Week 4 Day 22 (22 days after last daily PE) (± 1 day)	Week 5 Day 30 End of 30-day post-daily PE Period (± 1 day)			
Study drug administration (daily) b	x	x	x	x	x			
Corticosteroids	x	x	x	x	x			
Review of patient diary	x	x	x	x	x			
Neurologic assessments c	x				x	x	x	x
SMMSE	x				x	x	x	x
Clinically significant TTP event	x	x	x	x	x	x	x	x
Bleeding assessment d	x	x	x	x	x	x	x	x
Physical examination	x				x	x	x	x
Vital signs e	x				x	x	x	x
12-lead ECG f	x				x	x	x	x
Adverse events								→
Concomitant medication								→
Platelet count h	x	x	x	x	x	x	x	x
Clinical laboratory analyses g	x				x	x	x	x
Organ damage markers i	x	x	x	x	x	x	x	x
ADAMTS13 Activity	x	x	x	x	x	x	x	x
PK	x	x	x	x	x	x		
PD parameters j	x	x	x	x	x	x	x	x
Immunogenicity (ADA) k	x				x		x	x

a The following guidance with regard to timing of assessments planned at a single visit should be followed: 1) ECG and vital signs should be assessed prior to blood sampling, and 2) s.c. study drug should be dosed after all other assessments have been performed.

b Study drug is to be administered daily s.c. for 30 days. Of note, no study drug is to be administered at the Week 5 visit in case of no treatment extensions.

c Neurological assessment will include assessment of the neurological system (including coma, stupor, seizures, disorientation/confusion, hemiparesis/-plegia, focal deficit, agitation, dysarthria).

d Bleeding assessment is a clinical assessment of signs and symptoms of bleeding (e.g., petechiae, hematuria, epistaxis, meno-metrorrhagia, bruises) performed by the Investigator.

e Vital signs (assessment after 5 min in supine position): including blood pressure, pulse and temperature.

f To be performed after 5 min in supine position.

CONFIDENTIAL

- g Clinical laboratory analyses include blood chemistry, hematology and blood coagulation parameters.
- h Samples for platelet count will be assessed by a local laboratory.
- i Organ damage markers include LDH, Troponin I, creatinine.
- j PD parameters include RICO, vWF:Ag, and FVIII:C.
- k In case of a severe and/or serious hypersensitivity reaction, an additional blood sample to characterize the reaction should be collected as soon as possible after the start of the event.

Table 4: Time and events schedule for adults: Treatment extension period ^a

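### The Week 5 caplacizumab-placebo comparison of ADAMTS13 <10% keeps only subjects who have not switched to open-label drug, which biases it against caplacizumab

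*SAP*

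**What the plan says.** SAP 8.4 summarizes the share of subjects with ADAMTS13 activity below 10% at Week 5 in three columns (Caplacizumab, Placebo, OL Caplacizumab). It then fits a "logistic regression model with ADAMTS13 activity < 10% at Week 5 as dependent variable and treatment group (Caplacizumab, Placebo"), with the length of daily PE as the second covariate. Table 14.2.4.2 in SAP 14.5 calls for a "Frequency tabulation of number and percentage of subjects with ADAMTS13 activity <10% including Logistic regression results", repeated by rituximab and other immunosuppressive use.

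Four rules decide who is in that model:

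- **Crossover.** On a first exacerbation, "subjects will receive open label caplacizumab together with daily PE irrespective of what the initial treatment allocation was" (Protocol 3.1.1). The visit schedule then restarts.
- **Cut-off.** For the Caplacizumab and Placebo groups, "only data up to the switch are used in the analyses of these treatment groups" (SAP 4.3.6). In SAP 4.4.1, Table 1, the double-blind period of a switcher ends one minute before the "first administration datetime of OL treatment".
- **Timing.** The visit is headed "Week 5 Day 30 End of 30-day post-daily PE Period" (SAP Appendix A, Table 3), so it closes the window in which an exacerbation can occur.
- **Missing data.** "Missing values will not be included in the denominator count when computing percentages" (SAP 4.2.2), and SAP 4.2.4 imputes nothing unless stated otherwise.

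Elsewhere the SAP says so when it wants subjects followed in their initial arm through the switch: corticosteroids (5.5.1), total treatment duration (5.6), and PE and hospital days (6.2.2). The visible text of 8.4 does not.

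**The concern.** A subject who has an exacerbation and switches before Day 30 has no double-blind Week 5 value. That subject is absent from the regression and from the Caplacizumab-versus-Placebo contrast. The loss would be harmless if it were unrelated to ADAMTS13 and equal in the two arms. The protocol's own Phase II data suggest that it is neither.

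Protocol 1.2.4 reports exacerbations during treatment in 28% of placebo and 8% of caplacizumab subjects. It adds that "Seven of 8 placebo subjects with an exacerbation had ADAMTS13 activity <10% around the time of the exacerbation", while 14 of 16 placebo subjects without recurrence and with data were at 10% or above. On caplacizumab, 7 of the 8 relapsers were below 10% near the end of treatment but relapsed only after stopping drug, so subjects like them would still be counted at Week 5. Placebo would lose more of its low-ADAMTS13 subjects than caplacizumab does.

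Protocol 1.2.4 also raises the possibility that shorter PE on caplacizumab affected the timing of resolution of the autoimmune disorder. A Week 5 difference against caplacizumab would naturally be read in that light, and the planned model could not separate such an effect from the selection.

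**Working it through.** The plan gives no figure for this analysis. The Phase II rates do reproduce: 3/36 = 8.3% and 11/39 = 28.2%, matching the stated 8% and 28%.

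**Phase II counts (Protocol 1.2.4), low = ADAMTS13 <10%**

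- Placebo without recurrence: 16 − 14 = 2 of 16 low. Placebo exacerbators: 7 of 8 low.
- Caplacizumab without recurrence: 16 − 13 = 3 of 16 low. Relapsers after stopping drug: 7 of 8 low near the end of treatment. Together 10 of 24.
- Exacerbators left out: 10/24 = 41.7% vs 2/16 = 12.5%; OR = (10/14)/(2/14) = 5.0.
- Placebo exacerbators kept: 10/24 vs 9/24 = 37.5%; OR = (10/14)/(9/15) = 1.19.
- The 3 caplacizumab exacerbators, whose values are not stated, also kept: OR from (10/17)/(9/15) = 0.98 if none is low to (13/14)/(9/15) = 1.55 if all are.

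**Model for this trial with no drug effect on ADAMTS13**

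Protocol 3.1.2 expects no effect of the drug on the underlying trigger of the disease, so the null case is a reasonable reference. Inputs:

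- e, the share switching before Week 5: 8% caplacizumab, 28% placebo (Phase II).
- q, the share of switchers who are low: 7/8, taken from placebo and applied to both arms (assumption). It also assumes that status at exacerbation stands for what Week 5 would have shown.
- P, the true share low at Week 5, equal in both arms: not in the documents. I take 37.5% (the 9/24 above) as the base case and 30% to 55% as the range.

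Share low among those who remain = (P − e·q)/(1 − e), with e·q = 0.08 × 0.875 = 0.07 and 0.28 × 0.875 = 0.245.

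| P | Caplacizumab | Placebo | OR |
|---|---|---|---|
| 30% | 0.230/0.92 = 25.0% | 0.055/0.72 = 7.6% | 4.03 |
| 37.5% | 0.305/0.92 = 33.2% | 0.130/0.72 = 18.1% | 2.25 |
| 45% | 0.380/0.92 = 41.3% | 0.205/0.72 = 28.5% | 1.77 |
| 55% | 0.480/0.92 = 52.2% | 0.305/0.72 = 42.4% | 1.48 |

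With 66 randomized per arm, about 66 × 0.92 = 61 and 66 × 0.72 = 48 remain. An unadjusted two-sided comparison (normal approximation) would then give nominal p<0.05 against caplacizumab about 42% of the time at P = 37.5% (17% at P = 55%, 67% at P = 30%).

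**Sensitivity**

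- q from 0.7 to 1.0 over the same P: OR 1.20 to 11.0.
- e = 10% and 30% (the planning rates for the first key secondary composite, SAP 3.2), q = 7/8, P = 37.5%: OR 2.45.
- q = P, so that exacerbators are no more often low than others: OR 1.00. With q = 0.2 and P = 37.5% the bias reverses (OR 0.80), but 7/8 against 2/16 argues against both cases.
- A real benefit can offset the bias. With true shares of 25% (caplacizumab) and 37.5% (placebo), the planned contrast shows OR 1.10; with 20% and 37.5% it shows 0.75.

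**The case against.** Several points on the other side are sound.

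- Both arms lose their exacerbators, in the same direction. This is a difference in rate (8% vs 28%), not opposite selection.
- Switchers do not vanish. Those who reach open-label Week 5 are in the OL Caplacizumab column, and earlier values stay in the by-visit summary (Table 14.2.4.1). What is lost is the randomized contrast and the regression. The pooled OL column mixes both initial arms after a second course of PE and cannot restore them.
- The stated aim of the model is the effect of PE duration. A Cox model of time to sustained ADAMTS13 ≥10% is also planned (Table 14.2.4.3, Figure 14.2.4.2). The Week 5 model is therefore not the only look at ADAMTS13 recovery.
- Part of SAP 8.4 is blacked out, so handling of switchers there cannot be excluded. Table 14.2.4.2 shows none.
- The odds ratios above are unadjusted, whereas the planned model adjusts for PE duration and, per Table 14.2.4.2, includes an interaction. Whether the PE-duration coefficient is distorted was not calculated.
- The Phase II figures are small and uneven. Fisher p is 0.08 for 10/24 vs 2/16. Only 16 of 22 and 16 of 23 non-recurrent subjects had data; scaling the caplacizumab arm for this, (7 + 22 × 3/16)/30 = 37.1%, lowers the OR from 5.0 to about 4.1. Three exacerbations plus 8 relapses in 10 subjects suggests one is counted twice; 9/23 would give 4.5.

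These points limit the size and importance of the problem. None of them puts switchers back into the comparison.

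**Conclusion.** On the visible text, the Week 5 treatment contrast is conditional on not having switched, and that condition depends on both arm and outcome. If Phase II is a guide, it is biased towards more low ADAMTS13 on caplacizumab with no true effect: unadjusted OR about 2.25, range about 1.5 to 4.0 as the assumed true share <10% goes from 55% to 30%. This rests on the Phase II exacerbation rates, on 7/8 of switchers being low in both arms, and on equal true shares.

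A reader might infer that caplacizumab will appear to impair ADAMTS13 recovery, or that an odds ratio near 5 is to be expected. The documents do not support either. A true benefit could hide the bias, and 5.0 is an unadjusted ratio from small Phase II counts taken near the end of treatment rather than at Week 5. Nor need any difference seen be wholly artefact, since Protocol 1.2.4 itself allows for an effect of shorter PE.

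ADAMTS13 activity is not a primary or listed secondary endpoint and lies outside the testing hierarchy. This is a correction to an exploratory analysis and does not threaten the trial's main conclusions.

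**What to change.** In SAP 8.4 and Table 14.2.4.2:

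1. Add an analysis by initial randomized arm that retains subjects who recur and switch before Week 5, using their open-label Day 1 ADAMTS13 value. Appendix A, Table 2 already schedules that sample, before PE and before the i.v. dose.
2. As a check, add the composite of recurrence before Week 5 or ADAMTS13 <10% at Week 5, by initial arm.
3. If the open-label Day 1 value is missing, do not fall back on a Week 1 sample without flagging it. Week 1 is one day after the last daily PE, and SAP 5.3 notes that prior PE can substantially affect the level.
4. Keep the planned Week 5 model, labelled as conditional on reaching Week 5 without a switch.

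The cost is SAP wording, a derivation rule and the added output; no new sampling is needed. There is a downside to state in the plan. Values at recurrence are taken before Day 30, when there has been less time to recover, so they may overstate the share <10% in the arm with more exacerbations. The added analysis is therefore not free of bias, and both views should be shown side by side.
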